One of the proposed mechanisms for non-reassuring fetal heart tracings after initiation of analgesia is that the pain relief from neuraxial analgesia causes a decrease in catecholamine release by the sympathetic nervous system (5). The subsequent decrease in the circulating epinephrine concentration contributes to an increase in uterine tone, as epinephrine is a potent tocolytic agent. The increased tone, in turn, leads to a decrease in placental blood flow, and eventually fetal bradycardia.

The optimal oxytocin management in the peri-analgesia initiation period in terms of effects on uterine activity, uteroplacental perfusion, and fetal oxygenation, is not known. Anecdotally, some institutions arbitrarily decrease (or do not increase) the oxytocin infusion rate during initiation of analgesia. We hypothesize that decreasing the oxytocin infusion rate immediately before the initiation of CSE analgesia will cause fewer adverse fetal heart rate changes in the first 60 minutes following initiation of labor analgesia compared with maintaining the infusion rate.

3.0 Literature:

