4.0 Investigational Plan

.1 Study design: Double blinded randomized, controlled study.

.2 Methods:

.2.1 Size of study groups The primary endpoint is the incidence of non-reassuring fetal heart rate tracings after the placement of CSE. Group sample sizes of 162 in each of two groups 80% power to detect an effect size (W) of 0.1560 using a 1

degree of freedom Chi-Square Test with a significance level (alpha) of 0.05000. The incidence of fetal heart rate changes was estimated based on data from Kinsella, et al (11). The proportion of subjects with adverse fetal heart rate changes in the low-oxytocin and fluid bolus treatment group is estimated to be 8%, Therefore 350 patients will be enrolled to account for patient drop-out or ineligibility.

.2.2 Subject entry, exclusion and dropout criteria: Healthy nulliparous or multiparous women with a term ($37 \geq$ week gestation), singleton pregnancy in spontaneous labor or with spontaneous rupture of membranes, who request neuraxial analgesia, and who receive oxytocin augmentation per institutional protocols, will be eligible to participate in the study. Maternal exclusion criteria will include the presence of any systemic disease (e.g., diabetes mellitus, hypertension, preeclampsia); use of chronic analgesic medications; prior administration of systemic opioid labor analgesia; non-vertex presentation; scheduled induction of labor; or any contraindication to neuraxial analgesia.

.2.3 Protocol specific methods: Eligible women will be asked to participate shortly after admission to the Labor & Delivery Unit at Prentice Women’s Hospital during the routine pre-anesthetic interview. Informed, written consent will be obtained. Randomization based on a computer generated random number table; group assignments will be concealed in sealed, opaque envelopes. At the time of request for labor analgesia, group assignment will be determined by opening an opaque envelope. Patients will be randomized to one of two groups:

Group Assignment		Oxytocin Regimen
A		Routine oxytocin
B		Half-dose oxytocin

Fluid Management:

For patients in Groups A or B, an intravenous bolus of 500 mL LR will be initiated when the patient is positioned for CSE placement by the L & D nurse. The bolus will be administered through a free-flowing wide open intravenous catheter until complete.

Oxytocin Management:

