The Prentice Women's Hospital oxytocin augmentation protocols will be used. At the time of request for analgesia, if the patient is in group A the oxytocin management will continue as per the normal oxytocin protocol.

If the patient is randomized to groups B the dose of oxytocin currently being administered will be halved and not increased for the duration of the study period (60 minutes after the initiation of CSE). Care providers other than the Labor & Delivery nurse managing the fluid and oxytocin infusions, will be blinded to group assignment.

Analgesia Management:

All subjects will receive a maintenance infusion of 125 mL lactated Ringers (LR) solution throughout the study period as per Labor and Delivery protocol. Per institutional protocol, all patients will receive a 500 mL bolus of LR solution at the start of the neuraxial procedure ("wide-open rate") via the mainline IV. Labor analgesia will be initiated in the sitting position at the L3-4 or L2-3 interspace with a routine combined spinal-epidural (CSE) technique. The epidural space will be located with the loss of resistance technique and a 27-g x 5-in pencil point spinal needle will be passed through the epidural needle to the subarachnoid space. The intrathecal injection will consist of bupivacaine 2.5 mg and fentanyl 15 µg. A 20 gauge epidural catheter will be threaded and secured 4-5 cm in the epidural space. A test dose of 3 mL lidocaine 1.5% with epinephrine 1:200,000 will be administered through the epidural catheter. The epidural catheter will be

secured and the patient will be positioned in a lateral recumbent position. Patient-controlled epidural analgesia (PCEA) infusion of bupivacaine 0.0625% with fentanyl 1.95 µg/mL will be started at a rate of 8 mL/h with bolus dose = 8 mL, lock-out interval = 10 min and maximum volume = 32 mL/h.

Fetal heart rate monitoring:

Fetal heart rate monitoring and frequency of uterine contractions will be recorded by external tocodynamometry.

Treatment of hypotension:

Any decrease of 10% or greater from baseline in maternal systolic blood pressure after placement of the CSE will be treated by the IV administration of ephedrine or phenylephrine as guided by maternal heart rate, as per standard practice.

Treatment of non-reassuring fetal heart rate changes:

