If there are prolonged fetal heart rate decelerations, recurrent late decelerations, severe variable decelerations, or tachysystole, the Prentice Women's Hospital protocol for oxytocin management and intrauterine resuscitation will be followed.

Study completion:

The study is complete after 60 min after the intrathecal injection. After this time, obstetric and anesthesia management, including fluid and oxytocin management, will not be dictated by study protocol.

Fetal heart rate tracing assessment:

Fetal heart rate tracings will be examined for 30 minutes before and 60 minutes after the initiation of analgesia by a perinatologist blinded to study group off-line after delivery. NICHD guidelines (13) will be used to assess FHR patterns. Non-reassuring FHR patterns will be defined as any one or more of the following: minimal or absent variability, late decelerations, and persistent deceleration (see

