Appendix).

.2.4 Risks/Benefits: All of the techniques and medications used in this study are routinely used for CSE analgesia during labor and for management of labor. The risks of the CSE procedure itself are unchanged by participating in this study. These risks include: epidural analgesia may not be effective, the epidural procedure may need to be repeated, pruritus, nausea, vomiting, or hypotension. Less common risks include maternal postdural puncture headache. Rare complications include maternal or fetal respiratory depression, total spinal anesthesia, a toxic reaction to the anesthetic agents, and bleeding or infection in the epidural or spinal space that may lead to nerve damage. The risk of oxytocin administration includes nausea, vomiting, confusion, allergic reaction, uterine hyper stimulation, fetal bradycardia, or maternal cardiac arrhythmias. There are no direct benefits to the patient for participating in the study.

.2.4.1 Confidentiality:

The subjects' identity will be guarded by assigning a numerical code which is only known by the principal investigator. Data is stored in a department computer which is password protected. Each study subject will be assigned a study code number. The code will be used to link study data to patient identification (name) in a separate database. Subject data will be stored on secured computers at Northwestern University. Data access will be password protected and only available to study investigators. The data forms will be de-identified after the chart review prior to analysis. 7 years after manuscript the data both electronic and paper will be destroyed using the current departmental standards.

5.0 Data Analysis:

.1 Data collection form: The following data will be collected:

Demographic data: age, race, height, weight, gravidity, parity, and gestational age, history of prior inductions.

Labor data: time of rupture of membranes, cervical examination prior to placement of CSE (dilation, effacement, and station); start and stop time of fluid bolus, time of intrathecal injection, oxytocin dose at time of placement of CSE, vasopressor use and dose, maximum oxytocin dose in 60 minutes following placement of CSE, number of times oxytocin infusion is stopped or decreased for hyperstimulation or non-reassuring fetal status, time to complete cervical dilation, time of delivery, maximal maternal body temperature in study period.

Mode of delivery: normal spontaneous vaginal, instrumental vaginal, Cesarean.

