Neonatal data: 1- and 5-minute Apgar scores; fetal umbilical cord gases (if taken); birth weight; neonatal sepsis workup or ICU admission.

Fetal heart rate tracing data: see appendix

.2 Data evaluation:

The primary endpoint is the incidence of non-reassuring fetal heart rate tracings during the first 60 minutes after the placement of CSE. Cross tabulation tables will be constructed with the presence or absence of the endpoint as rows and the groups as columns. Differences in the frequency among groups will be assessed using a X^2 statistic. Exact tests will be computed using Monte-Carlo sampling of 10,000 samples with a confidence level of 99%. An interim data analysis will be conducted after completion of the first 175 evaluable participants.

Secondary outcomes and demographics: Age, height, weight, gestational age, fetal station, and frequency of contractions will be compared using ANOVA or Kruskal Wallis ANOVA with post-hoc comparisons correction for multiple comparisons. Binominal and ordinal data will be compared between groups using the X^2 statistic or the Fisher's exact test. A $P < 0.05$ will be required to reject the null hypothesis.

6.0 Interpretation of Anticipated Results:

We anticipate that the lower dose of oxytocin will cause fewer adverse fetal heart rate

changes in the first 60 minutes following initiation of labor analgesia.

7.0 Budget:

- .1 Materials:** No additional materials will be required as all of the materials used in the study are routinely used in the management of patients.
- .2 Labor Requirements:** Existing anesthesia personnel on Labor & Delivery Unit.
- .3 Presentation Cost:** Anticipated presentations at MARC, SOAP and ASA meetings.

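### Does lowering oxytocin in Group B before CSE placement spoil the 30-minute pre-analgesia tracing and the placement dose as baselines?

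*Combined protocol and SAP*

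**What the plan says.** Timing of the change is described in three places. The hypothesis in section 2.0, Background, concerns "decreasing the oxytocin infusion rate immediately before the initiation of CSE analgesia". Section 4.0 .2.3 fixes allocation at request: "At the time of request for labor analgesia, group assignment will be determined by opening an opaque envelope". The Oxytocin Management paragraph then opens with "At the time of request for analgesia, if the patient is in group A the oxytocin management will continue" under the usual protocol. For Group B it says that "the dose of oxytocin currently being administered will be halved and not increased for the duration of the study period", which ends 60 minutes after CSE initiation. The Group B sentence gives no start time of its own.

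The tracing window is counted from a different event: "Fetal heart rate tracings will be examined for 30 minutes before and 60 minutes after the initiation of analgesia".

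The data form (section 5.0 .1) lists "time of intrathecal injection, oxytocin dose at time of placement of CSE", the highest dose in the following hour, and the "number of times oxytocin infusion is stopped or decreased for hyperstimulation or non-reassuring fetal status". It lists neither the time of request nor the infusion rate before the assigned change.

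On analysis, section 5.0 .2 says: "The primary endpoint is the incidence of non-reassuring fetal heart rate tracings during the first 60 minutes after the placement of CSE". Contraction frequency is compared between groups in the paragraph that covers secondary outcomes and demographics together, with no time window.

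**The concern.** A baseline should be measured before treatment can act on it. If the Group B infusion is halved at request and the tracing window is counted back from CSE, some of the supposedly untreated half hour is treated, and in one group only. The oxytocin dose recorded at placement raises the same worry.

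Lower uterine activity or a calmer tracing in Group B before CSE could then be an early effect of the reduction and be mistaken for chance imbalance. A before/after contrast would understate the effect if part of it had already occurred. The report might also be unable to say for how long the rate had been lowered when analgesia began. Since the infusion rate is the only thing that differs by randomization, two descriptions of its start time look like a real defect.

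**Working it through.** **The plan's own figure.** Section 4.0 .2.1 gives 162 per group, W = 0.1560, alpha 0.05 and 80% power for a 1-df chi-square test. The noncentrality is N × W² = 324 × 0.1560² = 7.885, which gives power of 80.2%. The figure reproduces. Neither the pre-analgesia window nor the time of the oxytocin change enters it.

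**Share of the earlier tracing that is on treatment.** Let g be the minutes from request to CSE. The documents do not give g, so the values below are assumptions. If the change is at request, the share of the 30 minutes after assignment is min(g, 30)/30.

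| Assumed g (min) | Share after assignment | Untreated minutes left |
|---|---|---|
| about 0 (Background reading) | about 0% | about 30 |
| 5 | 5/30 = 17% | 25 |
| 20 | 20/30 = 67% | 10 |
| 30 | 30/30 = 100% | 0 |

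The range covers everything from nothing to the whole window, so it does not measure the size of any problem.

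**The dose at placement.** Take two women on the same rate r when the change is due, with no other adjustment before CSE. Group A is recorded at r and Group B at r/2, a ratio of 0.50. This is so whether the change is made at request or just before CSE, because both precede placement. The field is therefore wholly post-assignment in Group B on either reading, and settling the start time would not alter that. Doubling the Group B value recovers the earlier rate unless the infusion was also cut or stopped for another reason. The form counts such events, but the list attaches no time to them.

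**Which stated analyses use these quantities.**

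- Primary chi-square: uses the 60 minutes after CSE only. It compares randomized groups and is valid on either start time.
- Pre-analgesia tracing: section 5.0 .2 names no analysis of it.
- Placement dose: collected, but not among the variables named for comparison.
- Contraction frequency: a named comparison. It is exposed if taken before CSE on the request reading, and not if taken after CSE.

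One planned comparison is thus touched, and only under two conditions together.

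**The case for a change.** The strongest case for acting is that the start time defines the intervention, that the text gives it two ways, and that repair is cheap: a sentence on timing, a sentence on contraction frequency and two data fields. Contraction frequency also sits beside age, height and weight, so a reader could take it for a baseline, although the Background places uterine activity on the pathway from oxytocin to fetal heart rate. Doubling does not help in Group A, where the usual protocol may change the rate between request and CSE.

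Part of this stands. The Background and Methods wording must be reconciled to one start time, and the placement dose should not be labelled a baseline value.

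The rest does not support a change. The infusion rate at request is the wrong field to add if the change comes later, because the usual protocol may move the rate in between. Ending the earlier reading at envelope opening places it further from CSE and lengthens the tracing to be retrieved from 90 minutes to 30 + g + 60, or 95 to 120 minutes for g of 5 to 30, in order to protect a comparison that the plan does not make. The fetal heart rate appendix is not in the supplied text and may already define the pre-analgesia fields or a contraction window. Section 4.0 .2.4.1 mentions a chart review, so a field missing from the list is not proof that the information cannot be obtained.

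**Conclusion.** No change to the design, data or analysis is called for. The difference between the Background and the Methods is real but mild: one is a statement of hypothesis and the other gives the operative steps. It should be cleared up as a matter of wording, by the sponsor, and this review does not say which time is right.

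The effect on the primary result, sample size and power is nil. The share of the pre-analgesia tracing affected lies anywhere from about 0% to 100%, depending wholly on an interval that the documents do not give. The placement dose is halved in Group B by design. Both matter only if someone presents them as untreated baselines, which the plan does not propose. A sensible analyst would describe the placement dose as post-assignment, compare contraction frequency after CSE, and draw no balance conclusion from the earlier tracing without knowing when the rate was changed.

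This rests on section 5.0 .2 being the full list of analyses and on the unsupplied appendix adding no formal before/after comparison. If it did add one, the question would need to be reopened for that comparison alone.

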Appendix).

.2.4 Risks/Benefits: All of the techniques and medications used in this study are routinely used for CSE analgesia during labor and for management of labor. The risks of the CSE procedure itself are unchanged by participating in this study. These risks include: epidural analgesia may not be effective, the epidural procedure may need to be repeated, pruritus, nausea, vomiting, or hypotension. Less common risks include maternal postdural puncture headache. Rare complications include maternal or fetal respiratory depression, total spinal anesthesia, a toxic reaction to the anesthetic agents, and bleeding or infection in the epidural or spinal space that may lead to nerve damage. The risk of oxytocin administration includes nausea, vomiting, confusion, allergic reaction, uterine hyper stimulation, fetal bradycardia, or maternal cardiac arrhythmias. There are no direct benefits to the patient for participating in the study.

.2.4.1 Confidentiality:

The subjects' identity will be guarded by assigning a numerical code which is only known by the principal investigator. Data is stored in a department computer which is password protected. Each study subject will be assigned a study code number. The code will be used to link study data to patient identification (name) in a separate database. Subject data will be stored on secured computers at Northwestern University. Data access will be password protected and only available to study investigators. The data forms will be de-identified after the chart review prior to analysis. 7 years after manuscript the data both electronic and paper will be destroyed using the current departmental standards.

5.0 Data Analysis:

.1 Data collection form: The following data will be collected:

Demographic data: age, race, height, weight, gravidity, parity, and gestational age, history of prior inductions.

Labor data: time of rupture of membranes, cervical examination prior to placement of CSE (dilation, effacement, and station); start and stop time of fluid bolus, time of intrathecal injection, oxytocin dose at time of placement of CSE, vasopressor use and dose, maximum oxytocin dose in 60 minutes following placement of CSE, number of times oxytocin infusion is stopped or decreased for hyperstimulation or non-reassuring fetal status, time to complete cervical dilation, time of delivery, maximal maternal body temperature in study period.

Mode of delivery: normal spontaneous vaginal, instrumental vaginal, Cesarean.

Neonatal data: 1- and 5-minute Apgar scores; fetal umbilical cord gases (if taken); birth weight; neonatal sepsis workup or ICU admission.

Fetal heart rate tracing data: see appendix

.2 Data evaluation:

The primary endpoint is the incidence of non-reassuring fetal heart rate tracings during the first 60 minutes after the placement of CSE. Cross tabulation tables will be constructed with the presence or absence of the endpoint as rows and the groups as columns. Differences in the frequency among groups will be assessed using a X^2 statistic. Exact tests will be computed using Monte-Carlo sampling of 10,000 samples with a confidence level of 99%. An interim data analysis will be conducted after completion of the first 175 evaluable participants.

Secondary outcomes and demographics: Age, height, weight, gestational age, fetal station, and frequency of contractions will be compared using ANOVA or Kruskal Wallis ANOVA with post-hoc comparisons correction for multiple comparisons. Binominal and ordinal data will be compared between groups using the X^2 statistic or the Fisher's exact test. A $P < 0.05$ will be required to reject the null hypothesis.

6.0 Interpretation of Anticipated Results:

We anticipate that the lower dose of oxytocin will cause fewer adverse fetal heart rate

changes in the first 60 minutes following initiation of labor analgesia.

7.0 Budget:

- .1 Materials:** No additional materials will be required as all of the materials used in the study are routinely used in the management of patients.
- .2 Labor Requirements:** Existing anesthesia personnel on Labor & Delivery Unit.
- .3 Presentation Cost:** Anticipated presentations at MARC, SOAP and ASA meetings.

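### Does the plan's silence on whether the chi-square or the Monte-Carlo exact p-value decides the primary comparison undermine its stated 80% power?

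*Combined protocol and SAP*

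**What the plan says.** Section 4.0, Size of study groups, bases the sample size on one test: "Group sample sizes of 162 in each of two groups 80% power to detect an effect size (W) of 0.1560", the test being a 1 "degree of freedom Chi-Square Test with a significance level (alpha) of 0.05000". The low-oxytocin rate is put at 8%; the routine-group rate is not given. Enrolment is then raised above 324: "Therefore 350 patients will be enrolled to account for patient drop-out or ineligibility".

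Section 5.0, Data evaluation, describes the primary analysis in two consecutive sentences after the cross-tabulation. The first reads "Differences in the frequency among groups will be assessed using a X^2 statistic". The second reads "Exact tests will be computed using Monte-Carlo sampling of 10,000 samples with a confidence level of 99" percent. No word links them.

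The paragraph on secondary outcomes does offer alternatives: "Binominal and ordinal data will be compared between groups using the X^2 statistic or the Fisher's exact test". It also holds the only decision threshold in the analysis section: a P below 0.05 "will be required to reject the null hypothesis". That sentence does not name the test it applies to.

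**The concern.** Two readings are open. On the first, there is one procedure: a chi-square statistic whose p-value is obtained by Monte-Carlo sampling from its exact conditional distribution. On the second, an asymptotic chi-square p-value is reported with an exact p-value beside it.

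Each reading seems to leave a defect. On the first, the exact conditional test is more conservative than the asymptotic test used for sizing, so the stated 80% is not its power. On the second, the plan does not say which p-value is compared with 0.05, and a borderline result could be called either way after the data are seen. Sampling also adds noise that a 2x2 table does not require, because such a table can be enumerated completely, and there is no rule for a 99% interval that spans 0.05.

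At stake would be an overstated power figure, a data-driven choice of test, or both.

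**Working it through.** **Inputs.** From section 4.0: 162 per group (N = 324), W = 0.1560, two-sided alpha 0.05, low-oxytocin rate 8%, enrolment 350. From section 5.0: 10,000 Monte-Carlo samples, 99% confidence level. Assumption: the routine-group rate is back-solved from W and 8%.

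**Step 1: reproduce the plan's figure.** The noncentrality is N × W² = 324 × 0.1560² = 7.885. The noncentral chi-square with 1 degree of freedom gives power 80.2%. The stated 80% is therefore correct for the asymptotic chi-square test.

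**Step 2: routine-group rate.** For two equal groups, W = |p2 − p1| / (2 × √(p̄(1 − p̄))). With p1 = 0.08 and W = 0.1560, p2 = 0.1859. Check: p̄ = 0.1330, √(0.1330 × 0.8670) = 0.3395, and 0.1059 / (2 × 0.3395) = 0.156. The other root, 1.4%, runs against the trial's hypothesis and is not used.

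**Step 3: power by full enumeration.** All 2x2 outcomes were weighted by Binomial(n1, 0.08) × Binomial(n2, 0.1859). Each was tested with the uncorrected Pearson chi-square and with the exact conditional chi-square.

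| Half-dose / routine | Chi-square | Exact | Chi-square only |
|---|---|---|---|
| 162 / 162 | 81.6% | 76.8% | 4.7% |
| 161 / 163 | 81.5% | 78.1% | 3.4% |
| 163 / 161 | 81.6% | 80.0% | 1.6% |
| 160 / 164 | 81.1% | 79.4% | 1.8% |
| 164 / 160 | 81.9% | 79.2% | 2.7% |
| 173 / 173 | 84.2% | 80.2% | 4.0% |
| 175 / 175 | 84.5% | 80.7% | 3.8% |

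The last column is the chance that the chi-square is significant and the exact test is not. The reverse had probability 0 in every layout.

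Section 4.0 describes a computer-generated random number table and mentions no blocking. Under simple randomization (assumed), exactly 162/162 out of 324 arises in about 4% of trials. Averaged over the possible splits, exact power is 78.8% at 324 evaluable, which is 80 − 78.8 = 1.2 points below the stated figure, and 80.2% at 334. With exactly equal arms, 80% is first reached at 173 per group, or 346 evaluable.

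**Step 4: size at a single look.** At common rates of 8%, 13% and 18.6% with 162/162, the chi-square has size 4.9%, 5.0% and 5.0%; the exact test has 3.0%, 3.4% and 3.6%. With arms of 161/163 or 160/164, the exact test has 3.8 to 4.2%. Because the exact test never rejects alone, taking the smaller of the two p-values is the same as using the chi-square, so size stays at about 5%.

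**Step 5: a borderline table.** For 12/162 against 24/162, the chi-square is 324 × (12 × 138 − 24 × 150)² / (162 × 162 × 36 × 288) = 4.5, p = 0.034. The enumerated exact p is 0.0506.

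**Step 6: Monte-Carlo error.** The 99% half-width near p = 0.05 is 2.576 × √(0.05 × 0.95 / 10,000) = 0.0056. For the table in step 5, P(Binomial(10,000, 0.0506) ≤ 499) = 0.38, so 38% of runs would print a p-value below 0.05. Over all tables at the design rates, sampling puts the p-value on the wrong side of 0.05 in about 0.5% of trials, and the 99% interval spans 0.05 in about 3%.

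**Step 7: scale.** At 162/162, moving the unstated routine rate from 18% to 20% moves exact power from 72.3% to 85.6%, far more than the choice of test does.

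**The case for a change.** The strongest case for asking for a change is that both readings leave something unsaid, and one sentence would settle it. Nothing in the documents names the deciding p-value for the primary endpoint. The shortfall at 162/162 does not hang on the 8% assumption: with W held at 0.156 and the lower rate varied from 3% to 20%, exact power stays between 76.1% and 77.2%. The patients above 324 were added to cover losses, not to pay for a more conservative test. The two p-values can disagree, in 1.6 to 4.7% of trials at 324 evaluable, and that is where a choice made after seeing the data would matter.

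The observation and the arithmetic stand. The inference that the plan must change does not. The natural reading of the primary paragraph is a single procedure, a statistic followed by how its p-value is computed; the secondary paragraph says so with a conjunction when it means alternatives, and the primary paragraph does not. On that reading no choice between p-values arises. On the other reading, even the most favourable choice only returns the chi-square test at its nominal level. The 3-point shortfall needs exactly equal arms. The average gap of 1.2 points is smaller than the sizing formula's own error for the chi-square, which is 81.6 − 80.2 = 1.4 points. One part of the objection survives: if the full planned loss of 26 (350 − 324) occurs, an exact test would have about 1 point less power than stated on average.

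**Conclusion.** No change to the plan follows. The missing detail is one that an analyst can fill sensibly, and each way of filling it gives a valid single-look test of the primary endpoint. The stated 80% is right for the test the sizing paragraph names. If the exact p-value decides instead, power at 324 evaluable is about 77 to 80% depending on the split, averaging 78.8%, and it is back at 80% when about 334 (average over splits) to 346 (equal arms) of the 350 are evaluable. Using the chi-square keeps power and a size near 5%; using the exact test gives guaranteed conservatism for a point or so of power. That is a fair trade-off, and neither option clearly alters what the trial does or is likely to conclude. The Monte-Carlo settings are stated and valid, and affect about 0.5% of decisions.

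These figures assume a routine-group rate of 18.6% and, for the averages, simple randomization; if allocation is blocked to equal arms, the gap at 324 is 3.2 points (80 − 76.8). They cover a single look only. The interim analysis ("An interim data analysis will be conducted after completion of the first 175 evaluable participants") raises a separate question of error control that does not depend on which p-value is used.

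### The exact P value for the 2x2 primary table is to be simulated although it can be enumerated; if that simulated P decides, a result at the threshold depends on the random seed

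*Combined protocol and SAP*

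**What the plan says.** Section 5.0, .2 Data evaluation defines a binary primary outcome: "The primary endpoint is the incidence of non-reassuring fetal heart rate tracings during the first 60 minutes after the placement of CSE". It then sets out the table: "Cross tabulation tables will be constructed with the presence or absence of the endpoint as rows and the groups as columns". Section 4.0, .2.3 gives the number of columns: "Patients will be randomized to one of two groups". The primary table is therefore 2x2.

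Two sentences on testing follow in the primary-endpoint paragraph. The first is "Differences in the frequency among groups will be assessed using a X^2 statistic". The second is "Exact tests will be computed using Monte-Carlo sampling of 10,000 samples with a confidence level of 99" per cent. The section gives no random seed and no rule for a simulated interval that includes 0.05. It does not say which of the two P values decides.

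The threshold appears at the end of the next paragraph, on secondary outcomes: "A $P < 0.05$ will be required to reject the null hypothesis". It agrees with the sample-size statement in section 4.0, .2.1, which reads "Group sample sizes of 162 in each of two groups 80% power to detect an effect size (W) of 0.1560 using a 1" and continues "degree of freedom Chi-Square Test with a significance level (alpha) of 0.05000".

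**The concern.** Simulating an exact P value is useful when a table has too many possible arrangements to list. A 2x2 table with fixed margins has one free cell. With 162 women per group that cell takes at most 163 values (0 to 162), so the whole distribution can be listed in well under a second. The plan replaces an available exact number with a random estimate of it.

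If that estimate decides the primary endpoint, two analysts who follow the plan on the same data with different seeds could reach opposite conclusions when the result is close to 0.05. With no seed named in advance, the plan also offers no protection against rerunning until the preferred side appears.

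**Working it through.** **Inputs.** From section 4.0, .2.1: 162 per group, W = 0.1560, alpha 0.05, 80% power, and 8% in the low-oxytocin group. From section 5.0, .2: 10,000 samples and a 99% confidence level. The rate in the other group is not stated.

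**1. The plan's own sample size.** N = (1.960 + 0.842)² / 0.1560² = 322.5 in total, or 162 per group after rounding up. Power at N = 324 from the noncentral chi-square distribution is 80.2%. The stated figure is reproduced.

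**2. The missing rate (an assumption).** For equal groups, W = |p1 − p2| / (2√(p̄(1 − p̄))), where p̄ is the mean of the two rates. With p2 = 0.08 and W = 0.1560 this gives p1 = 0.186. Check: p̄ = 0.133 and 0.106 / (2 × 0.3395) = 0.156.

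**3. Simulation error at P = 0.05.** SE = √(0.05 × 0.95 / 10,000) = 0.0022. The 99% half-width is 2.576 × 0.00218 = 0.0056. The seed can therefore matter for exact P values from about 0.044 to 0.056.

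**4. Tables at the threshold.** The exact P is the sum of hypergeometric probabilities for all tables at least as far from equality as the one observed. The number of simulated tables at least that extreme is Binomial(10,000, exact P), and a run reports P < 0.05 when that number is 499 or less. For 24 against 12, the normal approximation gives z = (499.5 − 506.2) / 21.9 = −0.31, hence 0.38. The exact binomial results are:

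| Events (of 162 each) | Exact P, enumerated | Chance that one run lands on the wrong side of 0.05 | Pearson chi-square P |
|---|---|---|---|
| 28 vs 15 | 0.0484 | 24% | 0.033 |
| 24 vs 12 | 0.0506 | 38% | 0.034 |
| 20 vs 9 | 0.0501 | 48% | 0.032 |

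For 20 against 9, twenty seeds gave simulated P values from 0.0463 to 0.0544, with 9 of the 20 below 0.05.

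**5. Averaged over all possible tables, 162 per group.**

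| True rates | Exact P in the 0.044–0.056 band | One run on the wrong side | Two seeds disagree |
|---|---|---|---|
| 18.6% vs 8% | 2.7% | 0.48% | 0.69% |
| 8% vs 8% | 0.8% | 0.12% | 0.14% |

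With 175 per group (all 350 enrolled women evaluable), the wrong-side chance at 18.6% against 8% is 0.52%.

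**6. The neighbouring ambiguity, for scale.** The enumerated exact P and the Pearson P fall on opposite sides of 0.05 in 4.7% of trials at 18.6% against 8% (power 76.8% and 81.6%; 81.6 − 76.8 = 4.8 from the rounded figures). With 8% in both groups they do so in 2.0%. At the design alternative this is about ten times the seed effect (4.7 / 0.48 ≈ 10).

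**The case against.** The strongest reply is that the chi-square P may be the deciding one. The chi-square sentence comes first in the paragraph, and the trial is sized on a chi-square test with one degree of freedom. On that reading no seed enters the decision, and all three tables in step 4 are significant, with Pearson P from 0.032 to 0.034. This stands. A reader might infer that the primary verdict will depend on the seed whatever else is decided. The documents do not support that, because they leave open which P governs.

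A reader might also infer that the exact P cannot be reproduced. That goes too far. The documents do not mention a seed, but this does not show that it will go unrecorded. The 99% interval would also show the size of the error to anyone reading the report, although it would not settle a result whose interval includes 0.05.

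The Monte-Carlo sentence might be a general software setting meant for other tables. It stands in the primary-endpoint paragraph, however, directly after the description of the 2x2 table. Fisher's exact test is named only for binomial and ordinal data in the secondary paragraph, so it does not cure the primary analysis.

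Finally, Monte-Carlo exact testing is a valid procedure, and the effect here is small. Both statements are true. They limit the weight of the point without giving a reason to keep avoidable noise.

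**Conclusion.** The point holds as a free improvement of low weight. The primary exact P is to be simulated where full computation is immediate. If the simulated P decides, about 0.5% of trials at the design alternative and about 0.1% under no difference at 8% would land on the wrong side of 0.05. For particular tables at the threshold the chance is 24% to 48%, but those tables were chosen because they lie there and do not describe the typical trial. If the chi-square P decides, the verdict is unaffected and only the accompanying exact P carries simulation error.

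The overall figures assume 162 evaluable women per group, a single test at 0.05 (the planned interim look is ignored), a fresh seed for each run, and a rate of 18.6% in the routine-oxytocin group, which is derived from W and 8% and not stated. The table-specific figures need 162 per group and a fresh seed, but not the 18.6%. The unstated choice between the two P values matters more than the seed and should be settled in the same edit.

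**What to change.** Replace the Monte-Carlo sentence in section 5.0, .2 with wording such as: *The primary endpoint will be decided by [the Pearson chi-square P value / the exact P value; name one]. Exact P values for 2x2 tables will be obtained by full enumeration. Monte-Carlo sampling will be used only for larger tables where enumeration is not feasible, with a seed fixed in advance and recorded.*

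Either P value can be named. The chi-square matches the sample-size calculation; if the exact P is chosen, power at 162 per group is 76.8% under the assumed rates, and the plan should say so.

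The change costs one short edit to the analysis section and a different software option, with no extra participants, data or time. Keeping simulation and raising the number of samples is the poorer choice: a 99% half-width of 0.0005 at P = 0.05 would need 2.576² × 0.05 × 0.95 / 0.0005², or about 1.26 million samples, to approximate what enumeration gives exactly.
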